1.0 Specific Aims

Specific Aim 1: To test the hypothesis that GLP-1RA decreases intermuscular fat deposition in patients with stage 3-4 CKD.

Primary Outcome: We will measure intermuscular fat deposition by magnetic resonance imaging (MRI) before and after 12 weeks of dulaglutide 1.5 mg/wk. administration in patients with stage 3-4 CKD.

Specific Aim 2: To test the safety and feasibility of 12 weeks of dulaglutide 1.5 mg/wk administration as an adjunct therapy to the standard care of patients with stage 3-4 CKD.

Safety and tolerability will be evaluated throughout the study by assessment of weight change, hypoglycemic episodes, continuous glucose monitoring (only in patients with type 2 diabetes mellitus), serious adverse events (AE), treatment-emergent AE, discontinuations attributable to AE, laboratory tests, vital signs, 12-lead electrocardiograms, and allergic/hypersensitivity reactions.

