We will measure *in vivo* knee extensor's mitochondrial function using ³¹P-MRS to obtain the phosphocreatine recovery time constant, a measure of mitochondrial function, as we described previously⁶. During the 2 days prior to testing, we will ask that subjects 1) to perform no moderate or heavy intensity exercise within 1 day of testing; 2) not to consume alcohol within the 1 day prior to testing; 3) not to consume caffeine or use tobacco within 6 hours prior to testing; and 4) not to eat a meal 3-6 hours before testing. Mitochondrial function will be evaluated using the non-invasive technique ³¹P-MRS, which provides the quantification and kinetics of phosphocreatine (PCr), other phosphate-energy carrier molecules, and inorganic phosphate in limb muscles. Each subject will lie prone for approximately 30 minutes with a coil positioned over the belly of the vastus lateralis muscle. The position of the coil will be confirmed using scout localizer images and a reference positioned within the center of the coil (Figure 6.1.A).

[figure not shown]

Figure 6.1

After basal measurements, subjects will be asked to perform cycles of knee extension and rest using a research exercise device. Measurements will be recorded during the exercise protocol (approximately 90 seconds) and for additional 5 minutes (recovery period). We will repeat the exercise and recovery cycle at least two times. Spectra will be used to evaluate the kinetics of PCr. The primary endpoint will be the half-time of PCr recovery (time to achieve half of basal concentration during the recovery period). A spectra obtained by the investigators is shown in Figure 6.1.B. This method is reliable and reproducible and has been considered the “gold standard” to measure mitochondrial function^{7,8}.

Six-Minute Walk Test

On the same day of VUMC Nephrology Outpatient Clinic Visits, we will measure physical performance by the six-minute walk test. This test will be performed as previously

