Title of the study: Effects of Glucagon-Like Peptide-1 Agonists on Metabolism and Ectopic Fat Deposition in Chronic Kidney Disease: A Pilot and Feasibility Study

NCT number: NCT05254418

Date: 12/02/2024

Statistical Considerations

Sample size

Up to ten subjects will be enrolled to participate in the study. This study design will provide preliminary data on the effects of GLP-1RA on ectopic fat deposition, mitochondrial function, and physical performance in patients with CKD. We performed a power analysis based on the study by Neeland et al, investigating the effects of liraglutide on VAT in overweight and obese patients. According to their results, liraglutide treatment for a median of 36 weeks results in a mean change in VAT of 12.49%, with a standard deviation of 9.3%. Using their findings, we estimated the power for detecting changes in VAT based on a sample size of 10 using paired-t test (Figure 10.1). For a sample size of 10, there is adequate power to detect a mean change of 9% or more in VAT with a standard deviation of 9% and alpha value of 0.05.

Figure shows how the power would change if the sample size were to be extended to 20 following the pilot study.

[figure not shown]

Figure 10.1

[figure not shown]

Figure 10.2

Data Analysis

The comparison of primary and secondary outcomes, specifically the differences in (a) intermuscular fat deposition, (b) adipose tissue insulin resistance, (c) peripheral insulin resistance, (d) visceral tissue fat deposition, (e) phosphocreatine recovery time constant, (f) physical performance score, before and after dulaglutide administration will be assessed using Wilcoxon signed-rank tests.

Generalized linear mixed effects models will be used to examine associations of GLP-1RA with changes in outcomes with more than 2 repeated assessments. All p-values will be two-tailed ($\alpha=0.05$) and analyses will be completed using Stata 16.

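### The protocol defines the phosphocreatine recovery half-time against the resting level, so it is not a recovery half-time and does not match the time constant in the SAP

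*Protocol*

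**What the plan says.** The spectroscopy part of Protocol section 6.0 describes its outcome in two ways. It opens by saying that the technique is used "to obtain the phosphocreatine recovery time constant, a measure of mitochondrial function, as we described previously". After describing the exercise, it says: "The primary endpoint will be the half-time of PCr recovery (time to achieve half of basal concentration during the recovery period"). Basal measurements are taken before the knee-extension cycles, so basal means the resting level.

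The exercise bout is described by its length: "Measurements will be recorded during the exercise protocol (approximately 90 seconds) and for additional 5 minutes (recovery period"). The readable text gives no workload, target depletion, recovery model, or conversion between half-time and time constant.

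The SAP, under Data Analysis, lists "e) phosphocreatine recovery time constant" among the outcomes to be compared before and after dulaglutide with Wilcoxon signed-rank tests. Section 1.0 of the protocol gives the trial's primary outcome as intermuscular fat on MRI: "We will measure intermuscular fat deposition by magnetic resonance imaging (MRI) before and after 12 weeks of dulaglutide 1.5 mg/wk. administration".

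**The concern.** A recovery half-time is the time taken to regain half of what was lost. The protocol's bracket asks instead when PCr reaches half of its resting level. The two coincide only if exercise removes all of the PCr.

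The bracket is the only definition of the measure written out in either document, so someone working from the protocol would compute a different quantity from the one the SAP analyses. Two consequences follow. A scan in which exercise removes less than half of the PCr gives no value, and a missing value at either visit loses that participant's pair from the signed-rank test. In the remaining scans, a before/after difference combines any change in tau with any change in end-exercise depletion. Depletion can differ between visits for reasons unrelated to mitochondrial function, such as how hard the participant works.

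A smaller point is that the sentence calls this the primary endpoint. It probably means the main readout of the technique, but section 1.0 gives that status to intermuscular fat.

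**Working it through.** **Inputs.** The definitions come from Protocol section 6.0 and from the SAP's Data Analysis section. The documents give no figure for this endpoint, so there is none to reproduce. Depletion and tau are assumptions, because the readable text gives neither. I use depletion from 40% to 100% and tau from 30 to 60 s.

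**Model (assumed mono-exponential recovery to the resting level).** Let B be resting PCr, D the amount lost by the end of exercise, and d = D/B.

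PCr(t) = B − D × exp(−t/tau)

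**Usual half-time.** Half of the loss is restored when PCr(t) = B − D/2. Then exp(−t/tau) = 1/2 and t = tau × ln 2 = 0.693 × tau, whatever the value of d.

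**Endpoint as written.** Set PCr(t) = B/2. Then exp(−t/tau) = B/(2D) and t = tau × ln(2d).

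| Depletion d | Written endpoint ÷ tau | Usual half-time ÷ tau |
|---|---|---|
| below 50% | no value | 0.693 |
| 50% | 0 | 0.693 |
| 55% | ln 1.1 = 0.10 | 0.693 |
| 60% | ln 1.2 = 0.18 | 0.693 |
| 70% | ln 1.4 = 0.34 | 0.693 |
| 80% | ln 1.6 = 0.47 | 0.693 |
| 90% | ln 1.8 = 0.59 | 0.693 |
| 100% | ln 2 = 0.693 | 0.693 |

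The missing value below 50% does not depend on the exponential model. At 40% depletion, for example, PCr starts recovery at 0.60 of resting and never crosses one half.

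**Change in depletion with tau fixed (d from 60% to 70%).**

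| tau | Written endpoint | Usual half-time |
|---|---|---|
| 30 s | 5.5 → 10.1 s | 20.8 s, unchanged |
| 40 s | 7.3 → 13.5 s | 27.7 s, unchanged |
| 60 s | 10.9 → 20.2 s | 41.6 s, unchanged |

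The relative change is ln 1.4 / ln 1.2 = 1.85, or +85% at every tau. Further from the 50% point it is smaller: from 80% to 90%, ln 1.8 / ln 1.6 = 1.25, or +25%.

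**Tau improving by 20% (40 to 32 s) with a simultaneous rise in depletion.**

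- Usual half-time: 27.7 → 22.2 s, a fall of 20%.
- Written endpoint, d from 60% to 70%: 40 × ln 1.2 = 7.3 s → 32 × ln 1.4 = 10.8 s, a rise of 48%.
- Written endpoint, d from 80% to 90%: 40 × ln 1.6 = 18.80 s → 32 × ln 1.8 = 18.81 s, so the improvement disappears.

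**Effect on the planned test.** A correctly defined half-time is a constant multiple of tau. Multiplying every value by 0.693 leaves the signs and ranks of the paired differences unchanged, so for a given fit the signed-rank result is the same for either measure. The term half-time is therefore harmless, and the error lies in the words that tie it to the basal level. Lost pairs do matter: with five pairs, the smallest exact two-sided signed-rank p-value is 2/2⁵ = 0.0625, above the SAP's 0.05.

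**The case against.** The strongest reply is that this is loose drafting. The opening of the same protocol section and the SAP both name the time constant, the protocol cites the group's own published method for it, and only one bracket departs from that. The authors may have meant half of the recovery towards the basal level. The outcome is also one of six listed in the SAP, it is not primary, and the power calculation in the SAP is for visceral fat.

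Most of that is fair. The SAP names a sound quantity, and nothing in it calls for the bracketed one. The text does not say that half of the recovery was meant, however, and a citation does not override an explicit contrary definition beside it.

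The size of the distortion is also open to challenge. The +85% example lies near the 50% point, where percentages inflate, and the reversal of direction becomes no change at 80% to 90%. If depletion were the same at both visits and above 50%, the written endpoint would keep both the direction and the relative size of a change in tau. No passage says that depletion will shift. The exercise device and approximate bout length are the same throughout, although that does not fix depletion. The cited method may control it, and an example spectrum is in a figure that is not reproduced in the text available. These points limit what can be said about size. They do not rescue the definition, and the missing value below 50% depletion is unaffected by them.

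**Conclusion.** The concern holds. As written, the protocol's endpoint is not a recovery half-time, has no value when exercise removes less than half of resting PCr, depends on depletion above that level, and differs in substance from the time constant in the SAP.

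Under mono-exponential recovery, it ranges from 0 to 0.59 tau as depletion goes from 50% to 90%, against a constant 0.693 tau for the usual half-time. A 10-point shift in depletion at fixed tau changes it by +85% (60% to 70%) or +25% (80% to 90%). How often and how far this would affect the trial is unknown, because the readable text gives no depletion or tau values.

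This is a secondary outcome and the SAP already names the right quantity, so the correction should be made but does not threaten the trial's primary result.

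**What to change.** Replace the endpoint sentence in the 31P-MRS part of Protocol section 6.0 with wording such as:

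> The main 31P-MRS outcome, a secondary outcome of the trial, is the PCr recovery time constant, as in the SAP. If a half-time is reported, it is the time to restore half of the PCr depleted by the end of exercise (tau × ln 2).

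This also removes the clash with the primary outcome in section 1.0. As an option, report end-exercise PCr depletion by visit, so that readers can see whether it was stable.

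The cost is one protocol sentence. The SAP stays as it is, the same spectra are used, and no procedure is added.

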Title of the study: Effects of Glucagon-Like Peptide-1 Agonists on Metabolism and Ectopic Fat Deposition in Chronic Kidney Disease: A Pilot and Feasibility Study

NCT number: NCT05254418

Date: 12/02/2024

Statistical Considerations

Sample size

Up to ten subjects will be enrolled to participate in the study. This study design will provide preliminary data on the effects of GLP-1RA on ectopic fat deposition, mitochondrial function, and physical performance in patients with CKD. We performed a power analysis based on the study by Neeland et al, investigating the effects of liraglutide on VAT in overweight and obese patients. According to their results, liraglutide treatment for a median of 36 weeks results in a mean change in VAT of 12.49%, with a standard deviation of 9.3%. Using their findings, we estimated the power for detecting changes in VAT based on a sample size of 10 using paired-t test (Figure 10.1). For a sample size of 10, there is adequate power to detect a mean change of 9% or more in VAT with a standard deviation of 9% and alpha value of 0.05.

Figure shows how the power would change if the sample size were to be extended to 20 following the pilot study.

[figure not shown]

Figure 10.1

[figure not shown]

Figure 10.2

Data Analysis

The comparison of primary and secondary outcomes, specifically the differences in (a) intermuscular fat deposition, (b) adipose tissue insulin resistance, (c) peripheral insulin resistance, (d) visceral tissue fat deposition, (e) phosphocreatine recovery time constant, (f) physical performance score, before and after dulaglutide administration will be assessed using Wilcoxon signed-rank tests.

Generalized linear mixed effects models will be used to examine associations of GLP-1RA with changes in outcomes with more than 2 repeated assessments. All p-values will be two-tailed ($\alpha=0.05$) and analyses will be completed using Stata 16.

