3.0 Study Enrollment and Design

The study participants will be primarily selected from Vanderbilt's outpatient clinics and the Nashville Veterans Affairs outpatient clinics. The study visits will be conducted at the Vanderbilt University Medical Center (VUMC) Department of Nephrology Outpatient Clinic and Vanderbilt University Institute of Imaging Science (VUIIS). Institutional review board approval and written informed consent will be obtained from all study subjects. Patients meeting inclusion-exclusion criteria will be identified by physician investigators and coordinators. Patients will be first approached by clinical staff. Those who express interest will be informed about the study by the study personnel. The subjects will be selected based on the above inclusion/exclusion criteria.

[figure not shown]

Figure 5.1

All participants will undergo a 4-week run-in phase followed by 12 weeks of treatment (Dulaglutide 1.5 mg/wk), followed by 4 weeks of follow up after discontinuing the study medication (Figure 5.1).

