6.0 Study Procedures

After recruitment and review of eligibility, patients who gave informed consent will undergo the following procedures:

Screening Visit: Patients will have a screening visit 4 weeks prior to the beginning of the study intervention to confirm that they meet the inclusion-exclusion criteria. Subjects will be presented detailed information regarding the study with an opportunity to discuss the study as needed for a complete consent discussion. This visit will include a medical history extracted from the patients' medical records, demographic information, a medication history, HbA1c test (for patients with T2D), 12-lead electrocardiogram, vital signs and BMI measurement, urine, or blood pregnancy test (for females of childbearing potential) and serum creatinine test to confirm eGFR. Since the presence of any metal introduces unnecessary risk for MRI, a screening X-ray exam will be performed to confirm the absence of any metal in subjects where that is a possibility.

Visit 1 (Week -4): The purpose of this visit is to determine baseline characteristics of the patients enrolled. We will review medical records, obtain dietary and physical activity recalls

and 12-lead electrocardiogram. We will measure baseline vital signs and perform anthropometric measurements and scheduled blood and urine laboratory tests. We will calculate basal HOMA-IR, QUICKI, ADIPO-IR and LAR. We will perform MRI to assess basal visceral and ectopic fat distribution characteristics and ^{31}P MRS to assess basal skeletal muscle mitochondrial function. Baseline skeletal muscle endurance will be evaluated by six-minute walk test.

Visit 2 (Week 0): Prior to the first dose of the drug, we will review medical records, measure vital signs, perform anthropometric measurements, obtain 12-lead electrocardiogram, dietary and physical activity recalls, laboratory tests in blood and urine, six-minute walk test and perform MRI and ^{31}P MRS (Table 6.1).

The first dose of the study drug Dulaglutide (Trulicity®) will be administered while the participant is at the Nephrology Outpatient Clinic. Patients will be instructed on administration and given information about the instructions for use. Participants will administer dulaglutide on a weekly basis. Safety measures and compliance will be assessed for each patient by phone calls every two weeks.

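### Does the before-and-after test need a stated baseline visit, given that two MRIs precede the first dose?

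*SAP*

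**What the plan says.** The SAP, under Data Analysis, lists six outcomes, intermuscular fat (IMAT) first, and says that the differences "before and after dulaglutide administration will be assessed using Wilcoxon signed-rank tests". No visit is named. It adds mixed models for outcomes measured more than twice.

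The protocol gives the timing:

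- Specific Aim 1 measures IMAT by MRI "before and after 12 weeks of dulaglutide 1.5 mg/wk. administration in patients with stage 3-4 CKD".
- Section 3.0: "All participants will undergo a 4-week run-in phase followed by 12 weeks of treatment", then "4 weeks of follow up after discontinuing the study medication".
- Section 6.0, Visit 1 (Week -4): "The purpose of this visit is to determine baseline characteristics of the patients enrolled", and "We will perform MRI to assess basal visceral and ectopic fat distribution characteristics".
- Section 6.0, Visit 2 (Week 0): the procedures that precede the first dose include "laboratory tests in blood and urine, six-minute walk test and perform MRI".
- Section 6.0, Visits 3 and 4 (Weeks 12 and 16): each repeats the Week 0 procedures.

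Table 6.1 confirms MRI at all four visits. On sample size, the SAP says: "For a sample size of 10, there is adequate power to detect a mean change of 9% or more in VAT", with an SD of 9% and alpha of 0.05, using a paired t-test.

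**The concern.** A signed-rank test needs one untreated value per patient, and there are two candidates. The words baseline and basal are attached to the earlier one. If the Week -4 scan were used, the primary change would span 16 weeks, 4 of them without drug. With no control group, any drift in those weeks would be read as drug effect. If either scan is used alone, the other plays no part in the test, although power is borderline at n=10. Leaving the choice open until the data are seen would also allow selection in the primary result. The natural suggestion is to fix the baseline in advance as the mean of the two untreated scans, which costs no new visits and might gain precision.

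**Working it through.** **Which visit do the documents imply?** Treatment starts at Week 0 and lasts 12 weeks, so a change over 12 weeks of treatment is Week 12 minus Week 0. Visit 2 is explicitly placed before the first dose, and the post-treatment visits are defined by reference to Week 0. The Visit 1 wording describes patients at enrolment; it does not define an analysis baseline. This is an inference, because no sentence names the visit, but the pieces agree.

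**Reproducing the SAP's power.** Inputs from the SAP: mean change 9%, SD 9%, n=10, two-sided alpha 0.05. These are for visceral fat. Applying them to IMAT, and to the Week 0 to Week 12 change, is an assumption.

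- Paired t: noncentrality (9/9)×√10 = 3.162 on 9 degrees of freedom, power 80.3%. This agrees with the SAP's claim of adequate power, taken as about 80%.
- Exact signed-rank test: reject when the smaller rank sum is 8 or less (size 50/1024 = 0.0488). Simulated power with normal data is about 78.5%.

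**Other baselines.** Let V0 and V4 be the variances of change from Week 0 and from Week -4, and Vb the variance of the run-in change. For the mean of the two scans,

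Vm = (V4 + V0)/2 − Vb/4.

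Set V0 = 9² = 81. The documents give neither V4 nor Vb, so a range is needed. The mean effect is held at 9%, with no average run-in drift:

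| Assumption | V4 | Vb | Week -4: SD, power | Mean of two: SD, power |
|---|---|---|---|---|
| All visits equally correlated | 81 | 81 | 9.00, 78% | √60.75 = 7.79, 89% |
| Vb half of V0 | 81 | 40.5 | 9.00, 78% | √70.875 = 8.42, 84% |
| Vb a quarter of V0 | 81 | 20.25 | 9.00, 78% | √75.94 = 8.71, 81% |
| Random walk, no noise | 108 | 27 | 10.39, 67% | √87.75 = 9.37, 75% |
| Patient-specific linear trends, no noise | 144 | 9 | 12.00, 54% | √110.25 = 10.50, 65% |

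In the last row, changes from Week 0, from the mean baseline and from Week -4 span 12, 14 and 16 weeks, so the SD ratios to Week 0 are 14/12 = 1.167 and 16/12 = 1.333.

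The gain also shrinks if patients differ in their response to the drug. Suppose half of the 81 is response variation. Take the ratio of mean-baseline to Week 0 variance for the remainder as 0.75 (equal correlation) to 0.927 (the least favourable of three models combining decaying correlation with measurement noise). The SD is then √(40.5 + 40.5×0.75) = 8.42 to √(40.5 + 40.5×0.927) = 8.83, and power is about 84% to 80%.

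**Run-in drift with no drug effect.** Simulated false-positive rates of the signed-rank test, n=10, over equal correlation and the same three models; the shift is in units of the SD of the Week 0 to Week 12 change:

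| Run-in shift | Week -4 | Mean of two | Week 0 |
|---|---|---|---|
| 0.25 SD | 10–11% | 6.4–6.8% | 5% |
| 0.5 SD | 25–28% | 11–13% | 5% |

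**Six-minute walk.** Section 6.0 provides no practice test, so Week -4 is the first attempt within the study. Averaging it into the baseline would let half of any learning effect count as improvement on drug.

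**The case for a change.** The strongest case for a change is that the text really does leave the visit open, that the only scan called basal is the one least suited to Aim 1, and that a sentence would settle it. In a single-arm trial of up to ten patients, a choice made after seeing the data could matter. Week -4 is no better than Week 0 in any model above without average drift. Under correlation that falls over time but with appreciable measurement noise, the mean baseline still gives about 81% to 83%. The SAP also does not say how the off-drug Week 16 visit enters the mixed model.

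Most of this stands as description. The argument against Week -4 is sound, but it supports the reading that the documents already suggest. The argument for the mean baseline is weaker. Its gain depends on measurement noise making up enough of the run-in change (more than half of its variance in a random walk with noise), and nothing in the documents shows that. It also brings back half of the run-in drift that makes Week -4 unattractive. The Week -4 scan is not wasted: it shows directly whether patients were stable before treatment, and it can enter the mixed model. Keeping Week 16 as its own visit category there is ordinary practice.

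**Conclusion.** The omission is real but small. Week 12 minus Week 0 answers Aim 1 as written, keeps the test at its nominal size whatever happens in the run-in, and has about 78.5% power under the SAP's own inputs, close to the planned 80.3%. A mean baseline is a legitimate alternative with power of roughly 65% to 89% across the models shown. Against that possible gain, the false-positive rate is 11–13% instead of 5% if a run-in shift of half an SD occurs. Reasonable statisticians would divide on that trade-off, and in a pilot of up to ten patients neither choice is an error. The conclusion rests on three assumptions: that the visceral-fat figures carry over to IMAT, that the 9% SD belongs to the Week 0 to Week 12 change, and that pairs are complete and roughly normal. The reading of Week 0 as baseline depends on none of these. No change to the plan is called for.
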